10.3.4. Reporting of SAEs

SAE Reporting to Pfizer Safety via an Electronic DCT

- The primary mechanism for reporting an SAE to Pfizer Safety will be the electronic DCT.
- If the electronic system is unavailable, then the site will use the paper SAE DCT (see next section) to report the event within 24 hours.
- The site will enter the SAE data into the electronic DCT (eg, eSAE or PSSA) or paper form (as applicable) as soon as the data become available.
- After the study is completed at a given site, the electronic DCT will be taken off-line to prevent the entry of new data or changes to existing data.
- If a site receives a report of a new SAE from a study participant or receives updated data on a previously reported SAE after the electronic DCT has been taken off-line, then the site can report this information on a paper SAE form (see next section) or to Pfizer Safety by telephone.

SAE Reporting to Pfizer Safety via the CT SAE Report Form

- Facsimile transmission of the CT SAE Report Form is the preferred method to transmit this information to Pfizer Safety.
- In circumstances when the facsimile is not working, an alternative method should be used, eg, secured (Transport Layer Security) or password-protected email. If none of these methods can be used, notification by telephone is acceptable with a copy of the CT SAE Report Form sent by overnight mail or courier service.
- Initial notification via telephone does not replace the need for the investigator to complete and sign the CT SAE Report Form pages within the designated reporting time frames.

10.4. Appendix 4: Contraceptive and Barrier Guidance

10.4.1. Male Participant Reproductive Inclusion Criteria

No contraception methods are required for male participants in this study, as the calculated safety margin is ≥ 100 -fold between the estimated maternal exposure due to seminal transfer and the NOAEL for serious manifestations of developmental toxicity in nonclinical studies.

10.4.2. Female Participant Reproductive Inclusion Criteria

The criteria below are part of Inclusion Criterion 1 (Age and Sex; [Section 5.1](#)) and specify the reproductive requirements for including female participants. Refer to [Section 10.4.4](#) for a complete list of contraceptive methods permitted in the study.

A female participant is eligible to participate if she is not pregnant or breastfeeding and at least 1 of the following conditions applies:

- Is not a WOCBP (see definitions below in Section 10.4.3).

OR

- Is a WOCBP and agrees to use an acceptable contraceptive method during the intervention period (for a minimum of 28 days after the last dose of study intervention). The investigator should evaluate the effectiveness of the contraceptive method in relationship to the first dose of study intervention.

The investigator is responsible for review of medical history, menstrual history, and recent sexual activity to decrease the risk for inclusion of a woman with an early undetected pregnancy.

10.4.3. Woman of Childbearing Potential

A woman is considered fertile following menarche and until becoming postmenopausal unless permanently sterile (see below).

If fertility is unclear (eg, amenorrhea in adolescents or athletes) and a menstrual cycle cannot be confirmed before the first dose of study intervention, additional evaluation should be considered.

Women in the following categories are not considered WOCBP:

1. Premenarchal.
2. Premenopausal female with 1 of the following:
 - Documented hysterectomy;
 - Documented bilateral salpingectomy;

- Documented bilateral oophorectomy.

For individuals with permanent infertility due to a medical cause other than the above (eg, mullerian agenesis, androgen insensitivity), investigator discretion should be applied to determining study entry.

Note: Documentation for any of the above categories can come from the site personnel's review of the participant's medical records, medical examination, or medical history interview. The method of documentation should be recorded in the participant's medical record for the study.

3. Postmenopausal female.

- A postmenopausal state is defined as no menses for 12 months without an alternative medical cause. In addition:
 - A high FSH level in the postmenopausal range must be used to confirm a postmenopausal state in women under 60 years old and not using hormonal contraception or HRT.
 - A female on HRT and whose menopausal status is in doubt will be required to use one of the highly effective nonestrogen hormonal contraception methods if she wishes to continue her HRT during the study. Otherwise, she must discontinue HRT to allow confirmation of postmenopausal status before study enrollment.

10.4.4. Contraception Methods

Contraceptive use by men or women should be consistent with local availability/regulations regarding the use of contraceptive methods for those participating in clinical trials.

The following contraceptive methods are appropriate for this study:

Highly Effective Methods That Have Low User Dependency

1. Implantable progestogen-only hormone contraception associated with inhibition of ovulation.
2. Intrauterine device.
3. Intrauterine hormone-releasing system.
4. Bilateral tubal occlusion.
5. Vasectomized partner:
 - Vasectomized partner is a highly effective contraceptive method provided that the partner is the sole sexual partner of the WOCBP and the absence of sperm

has been confirmed. If not, an additional highly effective method of contraception should be used. The spermatogenesis cycle is approximately 90 days.

Highly Effective Methods That Are User Dependent

6. Combined (estrogen- and progestogen-containing) hormonal contraception associated with inhibition of ovulation:

- Oral;
- Intravaginal;
- Transdermal.

7. Progestogen-only hormone contraception associated with inhibition of ovulation:

- Oral;
- Injectable.

Sexual Abstinence

8. Sexual abstinence is considered a highly effective method only if defined as refraining from heterosexual intercourse during the entire period of risk associated with the study intervention. The reliability of sexual abstinence needs to be evaluated in relation to the duration of the study and the preferred and usual lifestyle of the participant.

Other Effective Methods

9. Progestogen-only oral hormonal contraception where inhibition of ovulation is not the primary mode of action.
10. Male or female condom, with or without spermicide.
11. Cervical cap, diaphragm, or sponge with spermicide.
12. A combination of male condom with either cervical cap, diaphragm, or sponge with spermicide (double-barrier methods).

10.5. Appendix 5: Liver Safety: Suggested Actions and Follow-Up Assessments

Potential Cases of Drug-Induced Liver Injury

Humans exposed to a drug who show no sign of liver injury (as determined by elevations in transaminases) are termed “tolerators,” while those who show transient liver injury but adapt are termed “adaptors.” In some participants, transaminase elevations are a harbinger of a more serious potential outcome. These participants fail to adapt and therefore are “susceptible” to progressive and serious liver injury, commonly referred to as DILI. Participants who experience a transaminase elevation above $3 \times$ ULN should be monitored more frequently to determine if they are “adaptors” or are “susceptible.”

In the majority of DILI cases, elevations in AST and/or ALT precede T bili elevations ($>2 \times$ ULN) by several days or weeks. The increase in T bili typically occurs while AST/ALT is/are still elevated above $3 \times$ ULN (ie, AST/ALT and T bili values will be elevated within the same laboratory sample). In rare instances, by the time T bili elevations are detected, AST/ALT values might have decreased. This occurrence is still regarded as a potential DILI. Therefore, abnormal elevations in either AST OR ALT in addition to T bili that meet the criteria outlined below are considered potential DILI (assessed per Hy’s law criteria) cases and should always be considered important medical events, even before all other possible causes of liver injury have been excluded.

The threshold of laboratory abnormalities for a potential DILI case depends on the participant’s individual baseline values and underlying conditions. Participants who present with the following laboratory abnormalities should be evaluated further as potential DILI (Hy’s law) cases to definitively determine the etiology of the abnormal laboratory values:

- Participants with AST/ALT and T bili baseline values within the normal range who subsequently present with AST OR ALT values $\geq 3 \times$ ULN AND a T bili value $\geq 2 \times$ ULN with no evidence of hemolysis and an alkaline phosphatase value $<2 \times$ ULN or not available.
- For participants with baseline AST **OR** ALT **OR** T bili values above the ULN, the following threshold values are used in the definition mentioned above, as needed, depending on which values are above the ULN at baseline:
 - Preexisting AST or ALT baseline values above the normal range: AST or ALT values ≥ 2 times the baseline values AND $\geq 3 \times$ ULN; or $\geq 8 \times$ ULN (whichever is smaller).
 - Preexisting values of T bili above the normal range: T bili level increased from baseline value by an amount of $\geq 1 \times$ ULN **or** if the value reaches $\geq 3 \times$ ULN (whichever is smaller).

Rises in AST/ALT and T bili separated by more than a few weeks should be assessed individually based on clinical judgment; any case where uncertainty remains as to whether it represents a potential Hy’s law case should be reviewed with the sponsor.

The participant should return to the investigator site and be evaluated as soon as possible, preferably within 48 hours from awareness of the abnormal results. This evaluation should include laboratory tests, detailed history, and physical assessment.

In addition to repeating measurements of AST and ALT and T bili for suspected Hy's law cases, additional laboratory tests should include albumin, CK, direct and indirect bilirubin, GGT, PT/INR, total bile acids, and alkaline phosphatase. Consideration should also be given to drawing a separate tube of clotted blood and an anticoagulated tube of blood for further testing, as needed, for further contemporaneous analyses at the time of the recognized initial abnormalities to determine etiology. A detailed history, including relevant information, such as review of ethanol, acetaminophen/paracetamol (either by itself or as a coformulated product in prescription or over-the-counter medications), recreational drug, or supplement (herbal) use and consumption, family history, sexual history, travel history, history of contact with a jaundiced person, surgery, blood transfusion, history of liver or allergic disease, and potential occupational exposure to chemicals, should be collected. Further testing for acute hepatitis A, B, C, D, and E infection, liver imaging (eg, biliary tract), and collection of blood samples for acetaminophen/paracetamol drug and/or protein adduct levels may be warranted.

All cases demonstrated on repeat testing as meeting the laboratory criteria of AST/ALT and T bili elevation defined above should be considered potential DILI (Hy's law) cases if no other reason for the LFT abnormalities has yet been found. **Such potential DILI (Hy's law) cases are to be reported as SAEs, irrespective of availability of all the results of the investigations performed to determine etiology of the LFT abnormalities.**

A potential DILI (Hy's law) case becomes a confirmed case only after all results of reasonable investigations have been received and have excluded an alternative etiology.

10.6. Appendix 6: ECG Findings of Potential Clinical Concern

ECG Findings That May Qualify as AEs

Marked sinus bradycardia (rate <40 bpm) lasting minutes.New PR interval prolongation >280 ms.New prolongation of QTcF to >480 ms (absolute) or by \geq60 ms from baseline.New-onset atrial flutter or fibrillation, with controlled ventricular response rate: ie, rate <120 bpm.New-onset type I second-degree (Wenckebach) AV block of >30 seconds' duration.Frequent PVCs, triplets, or short intervals (<30 seconds) of consecutive ventricular complexes.
ECG Findings That May Qualify as SAEs

QTcF prolongation >500 ms.New ST-T changes suggestive of myocardial ischemia.New-onset LBBB (QRS complex >120 ms).New-onset right bundle branch block (QRS complex >120 ms).Symptomatic bradycardia.Asystole:
In awake, symptom-free participants in sinus rhythm, with documented periods of asystole \geq3.0 seconds or any escape rate <40 bpm, or with an escape rhythm that is below the AV node.In awake, symptom-free participants with atrial fibrillation and bradycardia with 1 or more pauses of at least 5 seconds or longer.Atrial flutter or fibrillation, with rapid ventricular response rate: rapid = rate >120 bpm.Sustained supraventricular tachycardia (rate >120 bpm) ("sustained" = short duration with relevant symptoms or lasting >1 minute).Ventricular rhythms >30 seconds' duration, including idioventricular rhythm (HR <40 bpm), accelerated idioventricular rhythm (HR >40 bpm to <100 bpm),

and monomorphic/polymorphic ventricular tachycardia (HR >100 bpm [such as torsades de pointes]).

- Type II second-degree (Mobitz II) AV block.
- Complete (third-degree) heart block.

ECG Findings That Qualify as SAEs

- Change in pattern suggestive of new myocardial infarction.
- Sustained ventricular tachyarrhythmias (>30 seconds' duration).
- Second- or third-degree AV block requiring pacemaker placement.
- Asystolic pauses requiring pacemaker placement.
- Atrial flutter or fibrillation with rapid ventricular response requiring cardioversion.
- Ventricular fibrillation/flutter.
- At the discretion of the investigator, any arrhythmia classified as an adverse experience.

The enumerated list of major events of potential clinical concern are recommended as “alerts” or notifications from the core ECG laboratory to the investigator and Pfizer study team, and not to be considered as all-inclusive of what to be reported as AEs/SAEs.

10.7. Appendix 7: Abbreviations

The following is a list of abbreviations that may be used in the protocol.

Abbreviation	Term
Abs	absolute
ADL	activity/activities of daily living
ADME	Absorption Distribution Metabolism Excretion
AE	adverse event
ALC	absolute lymphocyte count
ALT	alanine aminotransferase
ANC	absolute neutrophil count
AST	aspartate aminotransferase
AUC	area under the concentration-time curve
AUC _{inf}	area under the plasma concentration-time profile from time 0 extrapolated to infinite time
AUC _{last}	area under the plasma concentration-time profile from time 0 to the time of the last quantifiable concentration (C _{last})
AV	atrioventricular
AxMP	auxiliary medicinal product
β-hCG	β-human chorionic gonadotropin
BMI	body mass index
BP	blood pressure
bpm	beats per minute
BUN	blood urea nitrogen
CFR	Code of Federal Regulations
CGRP	calcitonin gene-related peptide
CIOMS	Council for International Organizations of Medical Sciences
CK	creatine kinase
CL/F	apparent clearance
C _{last}	the last quantifiable concentration
C _{max}	maximum observed concentration
CO ₂	carbon dioxide (bicarbonate)
COVID-19	coronavirus disease 2019
CrCl	creatinine clearance
CRF	case report form
CRO	contract research organization
CRU	clinical research unit
CSR	Clinical Study Report
CT	calcitonin
CTIS	Clinical Trial Information System
CV	cardiovascular
CYP	cytochrome P450
DCT	data collection tool

Abbreviation	Term
DILI	drug-induced liver injury
EC	ethics committee
ECC	emergency contact card
ECG	electrocardiogram or electrocardiography
eCRF	electronic case report form
EDB	exposure during breastfeeding
E-DMC	External Data Monitoring Committee
EDP	exposure during pregnancy
eSAE	electronic serious adverse event
EU	European Union
EudraCT	European Union Drug Regulating Authorities Clinical Trials (European Clinical Trials Database)
FSH	follicle-stimulating hormone
F/U	follow-up
GCP	Good Clinical Practice
GGT	gamma-glutamyl transferase
HBsAg	hepatitis B surface antigen
HCVAb	hepatitis C antibody
HIV	human immunodeficiency virus
HR	heart rate
HRT	hormone replacement therapy
IB	Investigator's Brochure
ICD	Informed Consent Document
ICH	International Council for Harmonisation of Technical Requirements for Pharmaceuticals for Human Use
ID	identification
IMP	investigational medicinal product
IN	intranasal
IND	Investigational New Drug
INR	international normalized ratio
IP	investigational product
IPAL	Investigational Product Accountability Log
IPM	investigational product manual
IRB	Institutional Review Board
IV	intravenous
LBBB	left bundle branch block
LFT	liver function test
MOH	medication-overuse headache
MQI	medically qualified individual
NIMP	non-investigational medicinal product
NMPA	National Medical Products Administration
NOAEL	no observed adverse effect level
OTC	over-the-counter

Abbreviation	Term
PCP	phencyclidine
PE	physical examination
PI	Primary Investigator
PK	pharmacokinetic(s)
PPK	Population Pharmacokinetic
PSSA	Pfizer's Serious Adverse Event Submission Assistant
PVC	premature ventricular contraction/complex
QD	once daily
QTc	corrected QT interval
QTcF	QTc corrected using Fridericia's formula
RBC	red blood cell
SAE	serious adverse event
SAP	Statistical Analysis Plan
SARS-CoV-2	severe acute respiratory syndrome coronavirus 2
SoA	schedule of activities
SOP	standard operating procedure
SRSD	Single Reference Safety Document
SUSAR	Suspected Unexpected Serious Adverse Reaction
$t_{1/2}$	terminal half-life
T bili	total bilirubin
THC	tetrahydrocannabinol
ULN	upper limit of normal
T_{max}	time for C_{max}
TPPA	Treponema pallidum particle agglutination
US	United States
UTI	urinary tract infection
V_z/F	apparent volume of distribution
WBC	white blood cell
WOCBP	woman/women of childbearing potential

1. VERSION HISTORY

Table 1. Summary of Changes

Version/ Date	Associated Protocol Amendment	Rationale	Specific Changes
1 17 Apr 2023	Original 20 Feb 2023	N/A	N/A

2. INTRODUCTION

The purpose of the study is to evaluate the pharmacokinetics (PK), safety, and tolerability of zavegeptant following intranasal (IN) administration of 10 mg single dose in healthy Chinese adult participants. Results from this study will be used to support zavegeptant 10 mg IN China registration for the acute treatment of migraine.

This statistical analysis plan (SAP) provides the detailed methodology for summary and statistical analyses of the data collected in Study C5301009. This document may modify the plans outlined in the protocol; however, any major modifications of the primary endpoints definitions or their analyses will also be reflected in a protocol amendment.

2.1. Modifications to the Analysis Plan Described in the Protocol

Not Applicable.

2.2. Study Objectives, Endpoints, and Estimands

There are no estimands for this study.

Objectives	Endpoints
Primary:	Primary:

 To characterize the systemic exposure of zavegeptant following IN administration of 10 mg single dose in healthy Chinese adult participants. 	
 Zavegeptant plasma PK parameters: C_{max}, AUC_{last}, and AUC_{inf} as data permits
Secondary:	Secondary:

 To assess the safety and tolerability of zavegeptant following IN administration of 10 mg single dose in healthy Chinese adult participants. To characterize the plasma PK profile of zavegeptant following IN administration of 10 mg single dose in healthy Chinese adult participants. 	
 AEs, clinical safety laboratory tests, vital signs (BP and PR), physical examinations, and 12-lead ECGs. Additional zavegeptant plasma PK parameters: T_{max}, $t_{1/2}$, CL/F and Vz/F, as data permits

2.3. Study Design

This is a Phase 1, open-label, single dose study to characterize the PK, safety and tolerability of zavegeptant in healthy Chinese adults following a single intranasal dose of 10 mg.

Approximately 12 eligible participants, ages of 18 to 55 years (inclusive), will be enrolled in the study.

Screening evaluation will occur within 28 days prior to the study intervention administration (Day 1). Participants will be admitted to the clinical research unit (CRU) the day before Day 1 and will be kept under safety monitoring for 2 days at the CRU. Participants will receive 10 mg single dose of IN zavegeptant on Day 1. The PK of zavegeptant will be characterized following Day 1 dosing. A telephone follow-up will be made 28-35 days after the single dose.

This study will be conducted in a single center in China.

In this study, if more than 2 participants prematurely discontinue for reasons unrelated to the safety of the investigational product, participants may be replaced, at the discretion of the PI and sponsor study team.

3. ENDPOINTS AND BASELINE VARIABLES: DEFINITIONS AND CONVENTIONS

Samples for the PK analysis of zavegeptant will be taken according to the schedule of activities (SOA) given in the protocol.

Zavegeptant plasma PK parameters will be derived from the concentration-time profile using noncompartmental methods as detailed in Table 2. Actual PK sampling times will be used in the derivation of PK parameters. In the case that actual PK sampling times are not available, nominal PK sampling time will be used in the derivation of PK parameters.

Table 2. Zavegeptant Plasma PK Parameters

Parameter	Definition	Method of Determination
C_{\max}	Maximum plasma concentration	Observed directly from data
AUC_{last}	Area under the plasma concentration-time profile from time 0 to the time of the last quantifiable concentration (C_{last})	Linear/Log trapezoidal method
AUC_{inf}^a	Area under the plasma concentration-time profile from time 0 extrapolated to infinite time	$AUC_{\text{last}} + (C_{\text{last}}/k_{\text{el}})$, where C_{last} is the predicted plasma concentration at the last quantifiable time point estimated from the log-linear regression analysis

Table 2. Zavegepant Plasma PK Parameters

T_{max}	Time for C_{max}	Observed directly from data
$t_{1/2}^a$	Terminal half-life	$\log_e(2)/k_{el}$, where k_{el} is the terminal phase rate constant calculated by a linear regression of the log-linear concentration-time curve
CL/F^a	Apparent clearance	Dose/ AUC_{inf}
V_z/F^a	Apparent volume of distribution	Dose/($AUC_{inf} \times k_{el}$)

a. If data permit.

3.1. Primary Endpoint(s)

The primary endpoints are zavegepant plasma PK parameters:

- C_{max} , AUC_{last} , and AUC_{inf} as data permits.

3.2. Secondary Endpoint(s)

- AEs, clinical safety laboratory tests, vital signs (BP and PR), physical examinations, and 12-lead ECGs.
- Additional zavegepant plasma PK parameters: T_{max} , $t_{1/2}$, CL/F and V_z/F , as data permits

3.3. Other Endpoint(s)

There are no other endpoints in the study.

3.4. Baseline Variables

There are no baseline variables to be used as covariates or stratification factors in this study.

Baseline values are those collected on Day 1 prior to dosing, or the last pre-dose measurement collected on Day -1.

3.5. Safety Endpoints

3.5.1. Adverse Events

An adverse event (AE) is considered a Treatment-Emergent Adverse Event (TEAE) if the event started during the effective duration of treatment. All events that start on or after the first dosing day and time/start time, if collected, but before the end of the study will be flagged as TEAEs. The algorithm will not consider any events that started prior to the first dose date.

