8.4.1. Time Period and Frequency for Collecting AE and SAE Information

The time period for actively eliciting and collecting AEs and SAEs ("active collection period") for each participant begins from the time the participant provides informed consent, which is obtained before undergoing any study-related procedure and/or receiving study

intervention), through and including a minimum of 28 calendar days, except as indicated below, after the last administration of the study intervention.

Follow-up by the investigator continues throughout the active collection period and until the AE or SAE or its sequelae resolve or stabilize at a level acceptable to the investigator.

When a clinically important AE remains ongoing at the end of the active collection period, follow-up by the investigator continues until the AE or SAE or its sequelae resolve or stabilize at a level acceptable to the investigator and Pfizer concurs with that assessment.

For participants who are screen failures, the active collection period ends when screen failure status is determined.

If the participant withdraws from the study and also withdraws consent for the collection of future information, the active collection period ends when consent is withdrawn.

If a participant permanently discontinues or temporarily discontinues study because of an AE or SAE, the AE or SAE must be recorded on the CRF and the SAE reported using the CT SAE Report Form.

Investigators are not obligated to actively seek information on AEs or SAEs after the participant has concluded study participation. However, if the investigator learns of any SAE, including a death, at any time after a participant has completed the study, and they consider the event to be reasonably related to the study intervention, the investigator must promptly report the SAE to Pfizer using the CT SAE Report Form.

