10.3.1. Definition of AE

AE Definition

• An AE is any untoward medical occurrence in a patient or clinical study participant, temporally associated with the use of study intervention, whether or not considered related to the study intervention.• Note: An AE can therefore be any unfavorable and unintended sign (including an abnormal laboratory finding), symptom, or disease (new or exacerbated) temporally associated with the use of study intervention.

Events Meeting the AE Definition

• Any abnormal laboratory test results (hematology, clinical chemistry, or urinalysis) or other safety assessments (eg, ECG, radiological scans, vital sign measurements), including those that worsen from baseline, considered clinically significant in the medical and scientific judgment of the investigator. Any abnormal laboratory test results that meet any of the conditions below must be recorded as an AE:• Is associated with accompanying symptoms;• Requires additional diagnostic testing or medical/surgical intervention;• Leads to a change in study dosing (outside of any protocol-specified dose adjustments) or discontinuation from the study, significant additional concomitant drug treatment, or other therapy.• Exacerbation of a chronic or intermittent preexisting condition, including an increase in either frequency and/or intensity of the condition.• New condition detected or diagnosed after study intervention administration, even though it may have been present before the start of the study.• Signs, symptoms, or the clinical sequelae of a suspected drug-drug interaction.• Signs, symptoms, or the clinical sequelae of a suspected overdose of either study intervention or a concomitant medication. Overdose per se will not be reported as an AE or SAE unless it is an intentional overdose taken with possible suicidal/self-harming intent. Such overdoses should be reported regardless of sequelae.

Events NOT Meeting the AE Definition

- Any clinically significant abnormal laboratory findings or other abnormal safety assessments that are associated with the underlying disease, unless judged by the investigator to be more severe than expected for the participant's condition.
- The disease/disorder being studied or expected progression, signs, or symptoms of the disease/disorder being studied, unless more severe than expected for the participant's condition.

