- The investigator will also consult the IB and/or product information, for marketed products, in their assessment.
- For each AE or SAE, the investigator **must** document in the medical notes that they have reviewed the AE or SAE and have provided an assessment of causality.
- There may be situations in which an SAE has occurred and the investigator has minimal information to include in the initial report to the sponsor. However, **it is very important that the investigator always make an assessment of causality for every event before the initial transmission of the SAE data to the sponsor.**
- The investigator may change their opinion of causality in light of follow-up information and send an SAE follow-up report with the updated causality assessment.
- The causality assessment is one of the criteria used when determining regulatory reporting requirements.
- If the investigator does not know whether or not the study intervention caused the event, then the event will be handled as “related to study intervention” for reporting purposes, as defined by the sponsor. In addition, if the investigator determines that an SAE is associated with study procedures, the investigator must record this causal relationship in the source documents and CRF, and report such an assessment in the dedicated section of the CT SAE Report Form and in accordance with the SAE reporting requirements.

Follow-Up of AEs and SAEs

- The investigator is obligated to perform or arrange for the conduct of supplemental measurements and/or evaluations, as medically indicated or as requested by the sponsor, to elucidate the nature and/or causality of the AE or SAE as fully as possible. This may include additional laboratory tests or investigations, histopathological examinations, or consultation with other healthcare providers.

- New or updated information will be recorded in the originally submitted documents.
- The investigator will submit any updated SAE data to the sponsor within 24 hours of receipt of the information.

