6.5. Safety Summaries and Analyses

Standard summary tables and listings will be generated in accordance with CDISC standard within safety analysis set (as defined in Section 4).

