6.5.1. Adverse Events

All AEs will be coded according to the Medical Dictionary for Regulatory Activities (MedDRA) and will be listed and summarized.

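### The TEAE rule goes by onset alone, so an AE already open at dosing that worsens after the spray is not flagged if it stays as one record, and the AE summary does not name the flag

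*SAP*

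**What the plan says.** SAP 3.5.1 calls an AE treatment-emergent "if the event started during the effective duration of treatment". The working rule then flags "All events that start on or after the first dosing day and time/start time, if collected, but before the end of the study". It closes with: "The algorithm will not consider any events that started prior to the first dose date". Nothing in the section deals with a change in severity or seriousness.

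Protocol 8.4.1 says that active AE collection "begins from the time the participant provides informed consent". The Schedule of Activities places screening between Day -28 and Day -2 and starts AE monitoring there.

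Protocol 10.3.1 counts the following as an AE: "Exacerbation of a chronic or intermittent preexisting condition, including an increase in either frequency and/or intensity of the condition". For an event already reported, Protocol 10.3.3 says under follow-up: "New or updated information will be recorded in the originally submitted documents".

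On output, SAP 6.5 says: "Standard summary tables and listings will be generated in accordance with CDISC standard within safety analysis set". SAP 6.5.1 consists of one sentence: "All AEs will be coded according to the Medical Dictionary for Regulatory Activities (MedDRA) and will be listed and summarized". Neither section mentions the TEAE flag.

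**The concern.** A treatment-emergent count should capture two things: events that begin after dosing, and events already present that get worse after dosing. SAP 3.5.1 covers only the first. Take a mild headache recorded as an AE on Day -1 that becomes moderate after the spray. If the site updates the existing entry, the event keeps its Day -1 onset and cannot be flagged.

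The second issue runs the other way. The only AE summary that the SAP describes covers all AEs, and collection starts at consent. A dosed participant's screening-period event could therefore be counted in the same incidence table as events after the spray.

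Safety and tolerability is a secondary objective, and there is no control arm. Timing relative to the dose is thus the main way the tables can separate possible drug effects from background. Protocol 2.2.2.1 names mainly local events as the most frequent AEs to date (dysgeusia, throat irritation, nasal congestion, nasal discomfort), alongside nausea and back pain. Some of these are complaints a healthy volunteer might also report before dosing.

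**Working it through.** The documents give no figure on this point, so the check is mainly a comparison of rules.

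**Step 1: apply the rules to each kind of event.** The inputs are SAP 3.5.1 (flag), SAP 6.5.1 (summary), Protocol 8.4.1 (collection from consent), Protocol 10.3.1 (worsening as an AE) and Protocol 10.3.3 (updates to a reported event).

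| Event in a dosed participant | Recorded onset | Flagged under 3.5.1? | In the 6.5.1 summary as written? |
|---|---|---|---|
| A. New event after the spray | after dosing | yes | yes |
| B. Preexisting condition, not yet an AE on the CRF, worsens after dosing and is entered as an AE | after dosing | yes | yes |
| C. AE open at dosing, worsens, entered as a new record | after dosing (new record) | yes | yes |
| D. AE open at dosing, worsens, kept as one record | before dosing | **no** | yes, not distinguished from background |
| E. AE that began and ended before dosing | before dosing | no | **yes** |

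Row D is the gap in 3.5.1, and row E is the gap in 6.5.1.

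**Step 2: is C or D the likelier practice?** No section of either document tells the site to open a new record when intensity rises. The follow-up text in Protocol 10.3.3 points towards updating the existing entry, and the same section has each AE assigned to one intensity category. Protocol 8.3.2 has nasal symptoms and AEs recorded until they resolve. These point to D but do not settle it, because none of them addresses onset dates or new records on worsening.

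**Step 3: the boundary on Day 1.** The inclusion rule uses clock time only where it was collected, and the exclusion sentence works by date. A Day 1 event that began before the spray and has no start time would therefore be flagged. This is the opposite error to row D, unless the sponsor imputation rules cited in SAP 5.3.1 cover it.

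**Step 4: scale.** The input is n = 12 (Protocol 9.5).

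- Weight of one participant: 1/12 = 8.3 percentage points.
- Exact (Clopper-Pearson) 95% limits: 0/12 has an upper limit of 26.5%; 1/12 runs from 0.2% to 38.5%.
- Chance of at least one row-D participant among 12: 1 − (1 − p)^12, where p is the per-participant probability. The documents give no p, so the values below are assumptions.

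| Assumed p | 1 − (1 − p)^12 |
|---|---|
| 0.01 | 0.114 |
| 0.02 | 0.215 |
| 0.05 | 0.460 |
| 0.10 | 0.718 |

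The 8.3 points are the weight of any one participant in a study of this size. They do not measure the defect itself.

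**The case against.** A good deal can be said for the plan as it stands.

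- **The flag does most of its job.** It captures every event with a recorded post-dose onset, and the all-AE summary contains all of those events. A reader might infer that neither count measures what emerged on treatment. The documents do not support that: the flag is incomplete for one subtype, and the summary is a superset.
- **Worsening is not ignored.** A reader might also infer that anything present before dosing is lost even if the spray aggravates it. Protocol 10.3.1 makes exacerbation of a preexisting condition an AE in its own right, so row B is flagged. This objection stands and confines the gap to AEs already on the CRF at dosing.
- **The follow-up sentence in Protocol 10.3.3 is general.** It does not mention severity or onset, and Protocol 10.1.7 refers to a separate CRF Completion Requirements document that is not available here. That document may require a new record on worsening. This is why the point is conditional on one record being kept. It does not repair the SAP rule, which should not depend on a convention it does not state.
- **The flag may feed standard outputs.** A reader might infer from SAP 6.5.1 that no table will use it. SAP 6.5 calls for tables to a CDISC standard, which may include TEAE tables. Absence is not shown; the text only leaves it open.
- **The case is uncommon by design.** Exclusion criteria 3 and 9, with nasal inspection at screening, on Day -1 and before dosing, make an open nasal AE at dosing unlikely. The study is descriptive, all AEs are listed, and with 12 participants each can be read individually. This stands, and keeps the expected effect small.

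**Conclusion.** The point holds in a limited form. SAP 3.5.1 states an onset-only rule with no provision for worsening. An AE open at dosing that becomes more severe or serious after the spray is not flagged if the site keeps one record. As a weaker, second point, SAP 6.5.1 does not name the flag, so pre-dose events of dosed participants could enter the incidence table.

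The first part assumes that one record is kept, which the visible documents suggest but do not require. The second assumes that the CDISC-standard tables do not already restrict to TEAEs, which the SAP does not say. The expected effect is small: at most a participant or so, each worth 8.3 points at n = 12, with no documented rate from which to estimate more closely. The change is worth making because it costs almost nothing and settles before the data are seen which AE count is reported.

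**What to change.** **SAP 3.5.1.** Replace the closing exclusion sentence. Define a TEAE as an AE with onset at or after the Day 1 dosing time, or an AE with earlier onset whose severity or seriousness increases after dosing. The second part may instead be met by entering the worsening as a new record with its own post-dose onset.

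**SAP 6.5.1.** State that incidence tables use TEAEs and that AEs with pre-dose onset and no later worsening are listed only.

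**CRF completion instructions.** If they do not already say how to record a post-dose worsening, add one line. This matters because a record that holds a single intensity per AE cannot show a before-and-after change; in that case the new-record route is the one that works.

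The cost is a few SAP sentences, possibly one line for the site, and one extra derivation comparing severity and seriousness before and after dosing. Assessments, visits and participant numbers do not change.
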